3.3 Endpoints

The first primary endpoint variable will be the prevalence of persisting SARS-CoV-2 infection among the immunocompromised patients defined as the persistence or the recurrence of symptoms and signs (fever, dyspnea, hypoxemia, changes on chest-X ray or CT scan) and positive SARS-CoV-2 PCR ≥ 21 days after the time 0 (day of the first test positive for SARS-CoV2 infection).

The endpoints for the secondary objectives are:

- Duration of treatment carried out to address the persistent COVID-19 condition and treatment-related adverse effects.
- Duration of viral shedding, defined as the number of days between the first positive test and first negative PCR test.
- Duration of symptoms, defined as the number of days between symptoms onset and the clinical cure.
- Prevalence of imaging alterations, defined as the presence of new ground-glass and/or crazy paving and/or interstitial infiltrates at chest CT scan during the persisting infection (starting from 21 days after the first positive test until viral clearance).
- Re-infection within 120 days, define as new positive test with or without symptoms after viral clearance has been achieved.
- All-cause 120-day mortality.

4. Investigational plan

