4.4.3 Population size of the study and statistical power

According to the records of the Haematology Unit of IRCCS AOU of Bologna, from January 2022 to December 2022, 250 patients with underlying B cell malignancies have been diagnosed with SARS-CoV2 infection and we estimate that approximately 30% had viral shedding longer than 21 days. Thus, we deem that at the end of the study period, approximately 500 patients will be enrolled from IRCCS AOU of Bologna of which about 150 with prolonged infection. Considering the epidemiology of the other participating centers, we expect to reach an overall cohort of about 1000 immunocompromised patients with SARS-CoV-2 infection, with approximately 300 prolonged infections.

Power analysis carried out using Stata v.17.0 showed that a sample size of 1,000 allows to obtain power=80% and alpha=0.05 for a log-rank test comparing 120-days mortality, with a 300/700 allocation ratio, when the difference in mortality rates is at least 4% and mortality rate in the non-persistent COVID is as low as 3%, or when the difference in mortality rates is at least 5% and mortality rate in the non-persistent COVID is at least 4%.

Estimated sample sizes for two-sample comparison of survivor functions
 Log-rank test, Freedman method
 H0: HR = 1 versus Ha: HR != 1

alpha	power	N	N1	N2	nratio	E	delta	hratio	s1	s2	Pr_E
.05	.8	897	627	270	.43	59	2.054	2.054	.95	.9	.06503
.05	.8	1,343	939	404	.43	84	1.839	1.839	.95	.91	.06203
.05	.8	2,282	1,596	686	.43	135	1.626	1.626	.95	.92	.05902
.05	.8	4,900	3,426	1,474	.43	275	1.415	1.415	.95	.93	.05601
.05	.8	18662	13050	5,612	.43	990	1.206	1.206	.95	.94	.05301
.05	.843	.	1	1	.95	.95	.
.05	.8	561	392	169	.43	33	2.581	2.581	.96	.9	.05804
.05	.8	768	537	231	.43	43	2.31	2.31	.96	.91	.05503
.05	.8	1,140	797	343	.43	60	2.043	2.043	.96	.92	.05203

	.05	.8	1,918	1,341	577	.43	94	1.778	1.778	.96	.93	.04902	
	.05	.8	4,070	2,846	1,224	.43	188	1.516	1.516	.96	.94	.04601	
	.05	.8	15304	10702	4,602	.43	659	1.257	1.257	.96	.95	.04301	
	.05	.8	367	256	111	.43	19	3.459	3.459	.97	.9	.05105	
	.05	.8	471	329	142	.43	23	3.096	3.096	.97	.91	.04804	
	.05	.8	638	446	192	.43	29	2.737	2.737	.97	.92	.04503	
	.05	.8	933	652	281	.43	40	2.383	2.383	.97	.93	.04203	
	.05	.8	1,545	1,080	465	.43	61	2.031	2.031	.97	.94	.03902	
	.05	.8	3,221	2,252	969	.43	116	1.684	1.684	.97	.95	.03601	

s1, s2 = survival rates in groups 1 and 2
 N1, N2 = sample size required in groups 1 and 2.

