4.5 Study duration

The study will be composed by:

- a prospective recruitment period of 1 year after Ethics Committees' approvals and directorates' permissions to conduct the study (during which retrospective data will also be collected);
- Follow-up period of 120-days from the diagnosis of SARS-CoV-2 infection;
- Data collection and analysis, that will last 6 months

For an overall duration of approximately 22 months

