4.8 Statistical Analysis Plan

Patients' characteristics will be summarized using absolute frequencies and percentages (categorical variables) and mean±standard deviation or median and interquartile range (scale variables, according to their distribution).

The prevalence of persisting SARS-CoV-2 infection among the immunocompromised patients will be obtained as the ratio of the number of patients with evidence of persisting SARS-CoV-2 infection on the total number of enrolled patients.

As for the analysis of risk factors for persisting COVID, comparisons between COVID-persistent and non-persistent patients will be carried out by means of survival analyses for all outcomes expressed as durations (time-to-event analyses). These outcomes will be compared by estimating Kaplan-Meier curves, calculating log-rank tests and multiple Cox regressions in which COVID persistence will be the main risk factor and including the confounders and effect modifiers listed below.

- Age
- Sex
- Comorbidities (Charlson Comorbidity Index)
- Underlying hematologic disease state
- Chemotherapy treatments performed
- Duration of Hospital stay
- Admissions to intensive care
- Days with central venous catheter
- Bacterial and fungal superinfections
- Vaccination status
- Previous SARS-CoV-2 infections
- Serological status (anti-SARS-CoV-2 antibodies)

Re-infection and imaging alterations rates will be calculated as the ratio of the number of events to the overall number of patients, and the comparison between persisters and non-persisters will be carried out by calculating the corresponding risk ratios. A multiple logistic regression model will assess the relationship between exposure and re-infection (image alteration) net of the potential confounders.

For secondary aims, the secondary endpoints will be described just for the patients with persisting COVID, categorical variables will be reported as number and relative

frequencies, continuous variables will be reported as mean±SD or median and IQR according with their distribution.

5. Administrative procedures and declarations

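### The re-infection comparison ignores time at risk: persisters clear later within a fixed 120-day window, which by itself pulls the planned risk ratio downward

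*Combined protocol and SAP*

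**What the plan says.** Four parts of the combined protocol and SAP bear on this point.

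- **Endpoint (3.3).** "Re-infection within 120 days, define as new positive test with or without symptoms after viral clearance has been achieved". The origin of the 120 days is not stated. Clearance is not defined separately, but the neighbouring endpoint dates the end of shedding by one test: "Duration of viral shedding, defined as the number of days between the first positive test and first negative PCR test".
- **Exposure (3.3).** Persistence requires persisting or recurring symptoms or signs, together with "positive SARS-CoV-2 PCR ≥ 21 days after the time 0 (day of the first test positive for SARS-CoV2 infection").
- **Follow-up (4.5).** "Follow-up period of 120-days from the diagnosis of SARS-CoV-2 infection". The window therefore closes at the same point for everyone, whenever they clear.
- **Analysis (4.8).** "Re-infection and imaging alterations rates will be calculated as the ratio of the number of events to the overall number of patients"; then "the comparison between persisters and non-persisters will be carried out by calculating the corresponding risk ratios". The adjusted analysis is also binary: "A multiple logistic regression model will assess the relationship between exposure and re-infection (image alteration) net of the potential confounders".

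Section 4.8 plans survival methods only for outcomes expressed as durations. For re-infection it states no person-time, censoring, restriction to cleared patients or handling of death.

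**The concern.** Nobody can have a re-infection before clearing the first infection. Late clearance is part of what makes a patient a persister, so the exposure shortens the period in which the outcome can be seen. Patients still positive at day 120, or who die before clearing, stay in the denominator with no time at risk.

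The planned ratio therefore mixes two things: how likely a cleared patient is to be re-infected, and how much of the 120 days was left after clearance. Persisters could look protected when the post-clearance hazards are equal, and a real excess could be reduced or hidden. Adjustment for the covariates listed in 4.8 does not correct this, because none of them is time at risk.

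**Working it through.** **The plan's own figures.** None concerns re-infection. The table in 4.4.3 is for a log-rank test of 120-day mortality. Its legible rows reproduce to within one patient (for example 932 against the printed 933 for survival 0.97 vs 0.93), but they do not bear on this point.

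**Inputs from the documents.** At risk only after clearance (3.3); observation ends at day 120 from diagnosis (4.5); denominator is all patients (4.8); planned split 300 persisters and 700 non-persisters (4.4.3).

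**Assumptions.** Clearance day *c* in each group (P = persisters, N = non-persisters), and a constant re-infection hazard λ that is equal in both groups, so the true hazard ratio is 1.

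**Step 1: days at risk = 120 − c.** Clearance on day 12 leaves 108 days, day 45 leaves 75 and day 110 leaves 10. A patient who clears before day 21 has at least 100 days. One who is continuously positive to day 21 has at most 99.

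**Step 2: expected risk ratio at a low hazard = (120 − c_P)/(120 − c_N).**

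| Clearance day, P vs N | Days at risk | Expected ratio |
|---|---|---|
| 30 vs 18 | 90/102 | 0.88 |
| 45 vs 12 | 75/108 | 0.69 |
| 60 vs 10 | 60/110 | 0.55 |

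If 10% of persisters have not cleared by day 120, the middle row becomes 0.9 × 75/108 = 0.625.

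**Step 3: exact form, [1 − exp(−λ(120 − c_P))] / [1 − exp(−λ(120 − c_N))].** Take a 5% risk per 100 days at risk, so λ = −ln(0.95)/100 = 0.000513 per day, and c_N = 10. For c_P = 45 the risks are 0.0377 and 0.0549, ratio 0.69. For c_P = 21, 28, 60 and 90 the ratios are 0.90, 0.84, 0.55 and 0.28. Over hazards of 2% to 20% per 100 days, c_N from 7 to 20 and c_P from 21 to 90, the ratio runs from 0.99 to 0.27. It hardly depends on the hazard.

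**Step 4: a real excess.** Suppose the true hazard ratio is 1.5 and 5% of non-persisters are re-infected over their 110 days. The planned ratio is then expected to be 1.25, 1.02 or 0.82 for persisters clearing on day 28, 45 or 60.

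**Step 5: forces in the other direction.** Start from the step 3 case with ratio 0.69.

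- *Rebound counted as re-infection.* If this adds 2% of persisters, the ratio is (0.0377 + 0.02)/0.0549 = 1.05.
- *Recurrence moves patients between groups.* Expected events are 300 × 0.0377 = 11.32 and 700 × 0.0549 = 38.40. If 10% of the latter (3.84) are symptomatic recurrences at day 21 or later and are reclassified as persisters with their event, the risks are (11.32 + 3.84)/303.84 = 0.0499 and (38.40 − 3.84)/696.16 = 0.0496, ratio about 1.0.

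The 2% and 10% are assumptions too. They show only that modest amounts of either could cancel the downward pull.

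**The case against.** **The all-patient proportion is a legitimate quantity.** Re-infection within 120 days of diagnosis is a valid cumulative risk, and the secondary objective in 3.2 is to describe and compare. This stands for description. It does not rescue the comparison, because 4.8 treats persistence as an exposure and seeks its relationship to re-infection net of confounders, while late clearance is built into that exposure.

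**The 120 days might run from clearance.** Section 3.3 leaves this open. A patient clearing on day 45 would then need observation to day 165, but 4.5 stops at day 120. The observed time at risk is 120 − c on either reading.

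**Section 4.8 also says that secondary endpoints will be described only for patients with persisting COVID.** That sentence conflicts with the comparison planned in the same section and needs reconciling. It does not cancel the explicit risk ratio and logistic model.

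**The contrast may be smaller than illustrated.** Persistence requires symptoms or signs as well as a late positive PCR, so asymptomatic long shedders count as non-persisters and narrow the gap. This stands.

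**Chance may outweigh the shift.** If 2% are re-infected in each group (6 and 14 events), SE(log RR) = √(1/6 − 1/300 + 1/14 − 1/700) = 0.48, and the 95% limits lie a factor of about 2.6 either side. At 5% (15 and 35 events) the factor is about 1.8. A shift to 0.69 lies within both. That limits the weight of this secondary endpoint, but imprecision is no reason to keep a systematic distortion.

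**The net direction is not established.** A reader might infer that the reported ratio must fall below 1. The documents do not support that. Under 3.3 a re-infection is any new positive test after clearance, with no minimum interval or sequencing, and Section 2.1 names viral rebound as a high risk in patients of this kind. The persistence definition also admits recurrence at day 21 or later, with no upper limit. Both can push the ratio upward, as step 5 shows.

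**Conclusion.** The planned re-infection risk ratio and logistic model ignore a difference in time at risk that the exposure definition itself tends to create. Other things equal, this pulls the ratio downward: to about 0.88 to 0.55 under equal hazards for assumed clearance days of 30 vs 18 to 60 vs 10, and further if some persisters never clear. The size rests on assumed clearance days and a constant, equal hazard, since the documents give neither clearance times nor re-infection rates.

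The conclusion is about this one mechanism. It does not establish that the final ratio will be below 1, nor that a true excess would be reversed: with a true hazard ratio of 1.5 the expected value may still be above 1. The point concerns one secondary endpoint, and the sample size in 4.4.3 was calculated for mortality. It is worth correcting because the comparison as written cannot be read as susceptibility to re-infection after clearance.

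**What to change.** - **Section 3.3:** state whether the 120 days run from diagnosis or from clearance.
- **Section 4.8:** replace the re-infection risk ratio and logistic model with a time-to-event analysis starting at clearance, among patients with documented clearance. Use Cox regression or cumulative incidence, treat death as a competing event, and censor at day 120 from diagnosis.
- **Reporting:** give, by group, the number who never became at risk and the number with no documented negative PCR. Keep the proportion over all patients as a descriptive figure only.

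A rate ratio per person-day looks like a simpler alternative, but it equals 1 under no difference only if the hazard is constant after clearance. Late clearers contribute only early post-clearance days, so a hazard that changes with time since clearance would still distort it. The time-to-event form is preferable.

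**Costs.** The denominator falls below the full cohort. Selection is possible, because 4.3 leaves screening for persistence and management to routine practice and no clearance PCR is scheduled; patients who recover early may have no documented negative test. Clearance dates and death are already needed for shedding duration and 120-day mortality, but no other endpoint requires the re-infection date. The eCRF contents are not in the documents, so it must be confirmed that this date is collected; a change of SAP wording alone may not be enough.

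**What the change leaves open.** It does not settle the rebound and recurrence wording in 3.3, which needs its own clarification before the result can be interpreted.

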3.2 Secondary objectives

The secondary objective of the study is to describe and compare between patients with and without persisting COVID-19 the clinical, virological and radiological outcomes and the different therapeutic approaches performed.

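### Shedding and symptom durations in persisters are to be summarised by raw mean or median, although some will have no end date by day 120 and section 4.8 gives no rule for them

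*Combined protocol and SAP*

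**What the plan says.** Section 3.3 lists three durations among the secondary endpoints: treatment, viral shedding and symptoms. Shedding is given as "Duration of viral shedding, defined as the number of days between the first positive test and first negative PCR test". Symptom duration runs from onset to clinical cure. Section 4.5 sets a "Follow-up period of 120-days from the diagnosis of SARS-CoV-2 infection".

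Section 4.8 then handles durations in two places:

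- In the comparison of persisters with non-persisters, all outcomes expressed as durations are analysed by "estimating Kaplan-Meier curves, calculating log-rank tests and multiple Cox regressions".
- In its last paragraph, "For secondary aims, the secondary endpoints will be described just for the patients with persisting COVID", and "continuous variables will be reported as mean±SD or median and IQR according with their distribution".

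Neither place says how a patient enters who has no negative PCR or clinical cure by day 120, or who dies first.

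**The concern.** The three durations are the only continuous secondary endpoints in 3.3, so the raw mean or median rule applies to them and to nothing else on that list. Two of them, shedding and symptoms, are right-censored by design. A persister who is still PCR-positive at day 120, or who dies positive, has no shedding duration under the 3.3 definition. Taken literally, the value is missing and the summary covers completers only. The patients lost this way include the longest infections, which are the ones the study was set up to describe.

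Section 2.2 says the results may inform later trials and practice. A shedding time that is too short would carry over into follow-up lengths and sample sizes planned from it. The report could also give two different durations for the same group: one from the Kaplan-Meier curve and one from the raw table.

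**Working it through.** **The plan's own figures.** The plan gives no figure for durations. Its only design calculation is the mortality power table in 4.4.3, which reproduces. For survival 0.97 v 0.93 and ratio 0.43, HR = ln 0.93 / ln 0.97 = 2.383. Events = (1.960 + 0.842)² × ((1 + 0.43 × 2.383)/(1 − 2.383))² / 0.43 = 39.1. Event share = 0.0420, so N = 931 against 933 printed. This point does not affect that table.

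**Inputs.**
- From the documents: persistence starts at day 21 (3.3); follow-up ends at day 120 (4.5), leaving L = 99 days; deaths in persisters are 7% to 10%, taken from power scenarios in 4.4.3 (0.93 v 0.97, and 0.90 v 0.95).
- Assumed: clearance after day 21 is exponential with median m = 15, 30, 45 or 60 days, and deaths are independent at a constant rate from day 21. The documents give no clearance time and no share unresolved.

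**Formulas.** Let λ = ln 2/m, μ = −ln(1 − d)/99 with d the proportion dead, and h = λ + μ.
- No end date (dead or unresolved at day 120): 1 − (λ/h)(1 − e^(−99h))
- Completers-only quantile p: 21 − ln[1 − p(1 − e^(−99h))]/h
- Quantile p with unresolved patients entered at death or day 120: 21 − ln(1 − p)/h, capped at 120
- Mean on that second route: 21 + (1 − e^(−99h))/h
- Restricted mean time to clearance up to day 120: 21 + (1 − e^(−99λ))/λ
- Cumulative-incidence quantile with death competing: 21 − ln(1 − ph/λ)/h

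**Worked case, m = 45, d = 10%.** λ = 0.01540, μ = 0.00106, h = 0.01647, e^(−99h) = 0.196.
- No end date: 1 − 0.935 × 0.804 = 24.8%
- Completers-only median: 21 + 0.514/0.01647 = 52.2 days
- Entered at death or day 120: 21 + 0.693/0.01647 = 63.1 days
- Median time to clearance without death: 21 + 45 = 66 days
- Cumulative-incidence median: 21 + 0.765/0.01647 = 67.4 days

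**All cases, deaths 7-10%** (days; "entered" means unresolved patients entered at death or day 120)

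| m | No end date | True median | Completers median | Entered median | True upper quartile | Completers upper quartile | Entered upper quartile |
|---|---|---|---|---|---|---|---|
| 15 | 3% | 36 | 35.5-35.6 | 35.7-35.8 | 51 | 50 | 50-51 |
| 30 | 12-13% | 51 | 46 | 50 | 81 | 68-69 | 78-79 |
| 45 | 24-25% | 66 | 52 | 63-64 | 111 | 77 | 105-107 |
| 60 | 34-35% | 81 | 56 | 76-77 | not reached by day 120 | 82 | 120 (the cut-off) |

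**Means.** At m = 45, the completers' mean is about 58 days and the entered mean about 70. The restricted mean is 72, and the untruncated mean is 21 + 45/ln 2 = 86.

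**Cross-check by share unresolved, no deaths.** At 2% unresolved, the completers' median is 38.0 v 38.5 days. At 20% it is 52.3 v 63.5. Entering the unresolved at day 120 leaves that median at 63.5, but the mean is 70.1 v 82.4.

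**The case against.** The strongest reply is that censoring is not ignored in this plan. Section 4.8 already plans Kaplan-Meier curves for durations, and the persister curve yields a censored median. A reader might infer from the last paragraph that the plan overlooks unresolved patients altogether; the documents do not support that. What stands is narrower. The survival methods are attached to the comparison, the persister-only description has its own rule, and neither has a censoring or death rule.

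Second, no passage says that unresolved patients are to be dropped. If they are entered at death or day 120, the median is low by only about 1 to 5 days in the 30- to 60-day cases, and the mean is within about 1 to 3 days of the restricted mean. So it would be wrong to say that every raw summary is badly biased. The plan does not choose that route, however. The 3.3 definitions give such patients no value, and under that route the upper quartile can simply be the cut-off.

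Third, the calculation models shedding. Symptom duration shares the structure but starts at symptom onset, so its figures would differ. Treatment duration is not tied to clearance or cure: a course that ends at or before death is fully observed, and only treatment running at day 120 is cut off. The argument should not be extended to treatment as a whole.

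Finally, this is secondary description. It touches neither the primary prevalence estimate nor the sample size.

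**Conclusion.** The point holds as one that should be fixed, not as a fault that undermines the study. A raw mean or median is the wrong default for shedding and symptom duration in persisters, because patients who die unresolved or are unresolved at day 120 have no end date under 3.3.

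A reader might infer that the reported durations will be too short. The documents support only that they can be. If unresolved patients drop out, the median is low by about 5, 14 or 25 days when roughly 12-13%, 24-25% or 34-35% lack an end date. It is low by half a day or less when about 3% do. These sizes rest on exponential clearance after day 21, independent deaths at rates taken from power scenarios, and clearance times that the documents do not give. The direction is firmer than the size: under these assumptions the raw summaries come out correct or low, never high.

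**What to change.** In the last paragraph of 4.8:

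- Replace the raw summary of shedding and symptom duration in persisters with the median and quartiles read from the cumulative incidence curve of clearance or cure. Treat treatment duration the same way where treatment is still ongoing at day 120.
- Censor at day 120 or last contact, and treat death before resolution as a competing event.
- Report how many persisters were unresolved at day 120 and how many died unresolved.
- If a mean is wanted, give the restricted mean to day 120.
- State the estimand. A cumulative-incidence median with death competing is slightly longer than the median time to clearance without death (about 67 v 66 days at m = 45, and 83-84 v 81 at m = 60).

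Apply the same censoring rule to the Kaplan-Meier and Cox analyses in the comparison, and say there how death is handled, so that any difference between the two sets of durations is explained.

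The cost is SAP wording only, with no change to sample size. The downside is that some upper quartiles will be reported as not reached.
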